7.3.5. Electrocardiogram

TriPLICATE 12-lead ECGs will be measured in semi-supine position after 5 minutes rest and obtained at least 5 minutes apart on Day -1. Single 12-lead ECGs will be measured in semi-supine position after 5 minutes rest at all other time points during the study using an ECG machine that automatically calculates the heart rate and measures PR, QRS, QT, and QTc intervals. Refer to Section [5.4.2](#) for QTc stopping criteria and additional QTc readings that may be necessary.

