
 ● Reporting for tables, figures and formal statistical analyses : 
 ○ Planned time relative to dosing will be used in figures, summaries, statistical analyses and calculation of any derived parameters, unless otherwise stated. ○ The impact of any major deviation from the planned assessment times and/or scheduled visit days on the analyses and interpretation of the results will be assessed as appropriate. ● Reporting for Data Listings: 
 ○ Planned and actual time relative to study drug dosing will be shown in listings (Refer to IDSL Statistical Principle 5.05.1). ○ Unscheduled or unplanned readings will be presented within the subject's listings. ○ Visits outside the protocol defined time-windows (i.e. recorded as protocol deviations) will be included in listings but omitted from figures, summaries and statistical analyses. 	
Unscheduled Visits	

 ● Unscheduled visits will not be included in summary tables. ● Unscheduled visits will not be included in figures. ● All unscheduled visits will be included in listings. 	
Descriptive Summary Statistics	
Continuous Data	Refer to IDSL Statistical Principle 6.06.1
Categorical Data	N, n, frequency, %
Reporting of Pharmacokinetic Concentration Data	
Descriptive Summary Statistics	
Refer to IDSL Statistical Principle 6.06.1
 
 ● NQs at the beginning of a subject profile (i.e. before the first incidence of a measurable concentration) are deemed to be zero as it is assumed that in this circumstance no drug is yet measurable in the blood. ● For NQs at the end of the subject profile (i.e. after the last incidence of a measurable concentration); 
 ● for individual plots and pharmacokinetic analyses these are dropped (set to missing) as they do not provide any useful

Reporting Standards	

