10.4. Appendix 4: Derived and Transformed Data

10.4.1. General

Multiple Measurements at One Time Point

 Mean of the measurements will be calculated and used in any derivation of summary statistics but if listed, all data will be presented. If there are two values within a time window the value closest to the target day for that window will be used. If values are the same distance from the target then the mean will be taken. Subjects having both High and Low values for Normal Ranges at any post-baseline visits for safety parameters will be counted in both the High and Low categories of “Any visit post-baseline” row of related summary tables. This will also be applicable to relevant Potential Clinical Importance summary tables.
Study Day

 Calculated as the number of days from randomisation date: 
 Ref Date = Missing → Study Day = Missing Ref Date < Randomisation Date → Study Day = Ref Date – Randomisation Date Ref Date ≥ Randomisation Date → Study Day = Ref Date – (Randomisation Date) + 1

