10.11.5. Safety Tables

Safety Tables					
No.	Population	IDSL / TST ID / Example Shell	Title	Programming Notes	Deliverable [Priority]
Adverse Events					
2.1	Safety	AE1	Summary of All Adverse Events		IA [1], SAC [1]
2.2	Safety	AE1	Summary of All Drug- Related Adverse Events		IA [1], SAC [1]
2.3	Safety	AE15	Summary of Common (>=25%) Non-serious Adverse Events by System Organ Class and Preferred Term (Number of Subjects and Occurrences)		IA [1], SAC [1]
2.4	Safety	AE16	Summary of Serious Adverse Events by System Organ Class and Preferred Term (Number of Subjects and Occurrences)		IA [1], SAC [1]
Laboratory Measurements					
2.5	Safety	LB1	Summary of Clinical Chemistry Change from Baseline		SAC [1]
2.6	Safety	LB1	Summary of Haematology Change from Baseline		SAC [1]
2.7	Safety	UR3b	Summary of Urinalysis Dipstick Results		SAC [1]
Electrocardiograms					
2.8	Safety	EG1	Summary of ECG Findings		SAC [1]
2.9	Safety	SAFE_T1	Summary of Frequency of Maximum Post-Dose ECG Parameter Corrected QTc Interval		SAC [1]
2.10	Safety	SAFE_T2	Summary of Frequency of Maximum Change from Baseline for ECG Parameter Corrected QTc Interval		SAC [1]
2.11	Safety	EG2	Summary of Change from Baseline in ECG Values		SAC [1]
Vital Signs					
2.12	Safety	VS1	Summary of Change from Baseline in Vital Signs		SAC [1]

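### Tables 2.9 and 2.10 can miss a subject's worst QTc, because the SAP keeps unscheduled and out-of-window readings out of summaries with no exception for maxima

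*SAP*

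**What the plan says.** SAP 10.3.3 sets three handling rules for data off the planned schedule:

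- On timing: "Visits outside the protocol defined time-windows (i.e. recorded as protocol deviations) will be included in listings but omitted from figures, summaries and statistical analyses".
- On extra visits: "Unscheduled visits will not be included in summary tables". They are kept out of figures as well.
- On extra readings: "Unscheduled or unplanned readings will be presented within the subject's listings".

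SAP Appendix 11 (10.11.5) then lists two tables of extremes. Table 2.9 is the "Summary of Frequency of Maximum Post-Dose ECG Parameter Corrected QTc Interval" and Table 2.10 is the "Summary of Frequency of Maximum Change from Baseline for ECG Parameter Corrected QTc Interval". SAP 10.6.1 gives the bands: for absolute QTc, above 450 to 479, 480 to 499, and 500 msec or more; for increase from baseline, up to 30, above 30 to 59, and 60 msec or more.

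On several values close together, SAP 10.4.1 says "Mean of the measurements will be calculated and used in any derivation of summary statistics but if listed, all data will be presented" and "If there are two values within a time window the value closest to the target day for that window will be used". SAP 10.3.2.1 also averages replicates. For withdrawn subjects, SAP 10.5.1 admits planned data to the summaries.

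Protocol 9.4.2 commits to summarizing ECG abnormalities by group. It names QTc above 500 msec and a rise of at least 60 msec, and it does not limit this to scheduled readings. Protocol 7.3.5 foresees extra ECGs: "Refer to Section [5.4.2](#) for QTc stopping criteria and additional QTc readings that may be necessary". It schedules triplicates on Day -1 only and single ECGs at every other time.

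**The concern.** A rule that drops off-schedule values is sensible for means by time point, where an extra reading has no natural slot. It does not suit a maximum. A table of the highest post-dose QTc answers its own title only if every post-dose reading can count.

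Unscheduled ECGs are not a random sample of readings, since they tend to follow a high value or a symptom. Protocol 5.4.2 lets the QTc used for withdrawal be an average of triplicate ECGs. No post-dose triplicate is scheduled, so such a set would itself be off schedule. A subject could then meet a QTc withdrawal criterion on readings that never reach Table 2.9 or 2.10.

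Safety is a secondary objective in every part, QT prolongation is a named risk in Protocol 4.6.1, and the cohorts are small enough for one subject to alter a category percentage visibly.

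**Working it through.** The plan states no figure to reproduce, because this is a data-handling rule. The check has four steps.

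**1. Does any rule keep the worst value?** There are four ways in which a post-dose repeat ECG might be handled:

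- Unscheduled visit: excluded from summary tables (SAP 10.3.3).
- Visit outside its window: excluded from summaries (SAP 10.3.3).
- Replicate at the same time point: averaged (SAP 10.3.2.1 and 10.4.1).
- Second value in a window: the one nearest the target is used (SAP 10.4.1).

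None of the four guarantees that the highest reading is used. SAP 2.1 declares one departure from the protocol's analysis, the Part 3 power model, so a narrowing of the ECG summary in Protocol 9.4.2 is not declared.

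**2. What happens to one subject?** These readings are hypothetical: baseline 425, highest scheduled post-dose value 478, unscheduled repeat 503 msec. The bands are those of SAP 10.6.1.

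| Handling of the repeat | Maximum | Table 2.9 band | Change | Table 2.10 band |
|---|---|---|---|---|
| Dropped | 478 | >450 to 479 | 478 − 425 = 53 | >30 to 59 |
| Averaged | (478 + 503)/2 = 490.5 | 480 to 499 | 490.5 − 425 = 65.5 | ≥60 |
| All readings count | 503 | ≥500 | 503 − 425 = 78 | ≥60 |

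The same subject falls into three different absolute bands, depending on a choice that the SAP does not settle for this table.

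**3. How much does one subject weigh?** Part 3 randomizes 10 to active and 2 to placebo (Protocol 9.2.1): 1/10 = 10 percentage points of the active subjects. Part 1a enrols about 27: 1/27 = 3.7 points.

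**4. How often would a repeat be the worst reading?** The documents do not say. As an illustration, a normal simulation took mean QTc 425 msec and a repeat triggered by a scheduled value above 450 msec. It varied the between-subject SD, the single-reading SD and the true rise by the time of the repeat. All of these are assumptions. The entries are the proportion of triggered repeats that exceed the scheduled trigger.

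| Between-subject SD | Reading SD | Rise 0 | Rise 5 | Rise 10 |
|---|---|---|---|---|
| 12 | 6 | 0.230 | 0.447 | 0.688 |
| 12 | 10 | 0.156 | 0.269 | 0.409 |
| 18 | 6 | 0.343 | 0.578 | 0.786 |
| 18 | 10 | 0.269 | 0.403 | 0.552 |

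That is about 16% to 34% if the true QTc is stable and 27% to 79% if it is still rising by 5 to 10 msec. With a stable QTc the repeat is usually lower than its trigger, and the trigger stays in the tables. So the rule changes a maximum in some subjects and leaves it unchanged in others.

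**The case against.** The strongest reply is that little is lost and much is uncertain.

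- **Nothing is hidden.** Unscheduled readings are listed, and Listings 31 to 33 cover ECG values and changes of potential clinical importance. ECG findings judged clinically significant are adverse events, and the adverse event tables are not built by visit. This stands: the defect lies in the summary tables, not in the record.
- **Exclusion is not certain.** One rule speaks of visits, while subjects are confined to the unit through the dosing periods. A prompt repeat might be treated as a replicate and averaged. The documents give no numeric ECG window, so a late ECG cannot be identified from them. This also stands, but averaging does not preserve a maximum either.
- **Unseen sources may settle it.** The shells for the two tables and the sponsor's reporting standards are not in the documents and could define which readings count. That is possible, but the SAP text itself makes no exception.
- **More readings mean more chances of a high one.** Taking the maximum over extra readings in flagged subjects raises their expected maximum. This is a real cost of the fix, to be disclosed.
- **Safety ECGs are treated differently.** Protocol 5.4.2 holds each subject to one correction formula but exempts safety and non-protocol ECGs. Pooling them carelessly could mix formulas within one maximum, so the fix has to address this.

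A reader might also infer that all the safety tables, or the laboratory results, are biased. The display list does not support that. Only Tables 2.9 and 2.10 are titled as maxima. The laboratory, vital-sign and ECG change tables are change-from-baseline summaries, where the exclusion is reasonable. Laboratory toxicities of Grade 3 or higher go to listings. Nor does the protocol order repeat ECGs: it says only that they may be needed.

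**Conclusion.** The point holds for Tables 2.9 and 2.10. Followed as written, SAP 10.3.3 can place a subject whose worst post-dose QTc was unscheduled or late in too low a category. That can leave a QTc above 500 msec or a rise of at least 60 msec out of the by-group summary in Protocol 9.4.2. No other SAP rule keeps the worst value. The consequence is a possible error in a count, worth 10 percentage points per subject among the Part 3 active subjects. It occurs only if the excluded reading is that subject's worst.

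A reader might infer a fixed downward bias from the expected gap between the larger of two readings and a single one: SD/√π = 0.564 SD, or 4.5 msec at an assumed SD of 8 and 5.6 msec at 10. That should not be claimed. The formula is for two independent, unselected readings. Here a scheduled abnormal value that prompts a repeat remains in the table, and the documents give no reading SD.

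**What to change.** Keep the exclusion for by-time-point summaries. Add to SAP 10.3.3 that Tables 2.9 and 2.10 use all post-dose readings up to the next dose, including unscheduled and out-of-window ones. Apply the same sentence to any potential-clinical-importance count or any-post-baseline row of the kind mentioned in SAP 10.4.1, if one is produced. The sentence should also settle two details:

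- Each subject's QTc enters under the same correction formula throughout. SAP 10.4.3 already provides for deriving a missing QTcB or QTcF when the RR interval is available.
- State whether a triplicate set enters as its average or as separate traces.

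Add a footnote to both tables giving the number of unscheduled readings by group, so that a reader can see where extra readings gave more chances of a high value. The cost is the added SAP text, a programming flag and the footnote. No extra data are collected.

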10.4. Appendix 4: Derived and Transformed Data

10.4.1. General

Multiple Measurements at One Time Point

 Mean of the measurements will be calculated and used in any derivation of summary statistics but if listed, all data will be presented. If there are two values within a time window the value closest to the target day for that window will be used. If values are the same distance from the target then the mean will be taken. Subjects having both High and Low values for Normal Ranges at any post-baseline visits for safety parameters will be counted in both the High and Low categories of “Any visit post-baseline” row of related summary tables. This will also be applicable to relevant Potential Clinical Importance summary tables.
Study Day

 Calculated as the number of days from randomisation date: 
 Ref Date = Missing → Study Day = Missing Ref Date < Randomisation Date → Study Day = Ref Date – Randomisation Date Ref Date ≥ Randomisation Date → Study Day = Ref Date – (Randomisation Date) + 1

10.4.2. Study Population

Demographics
Age

 GSK standard IDSL algorithms will be used for calculating age where birth date is imputed as: 
 Any subject with a missing day will have this imputed as day ‘15’. Any subject with a missing date and month will have this imputed as ‘30th June’. Birth date will be presented in listings as ‘YYYY’.
Body Mass Index (BMI)

 Calculated as Weight (kg) / [Height (m)]²

10.4.3. Safety

ECG Parameters
RR Interval

 If ECG values are machine read and either RR interval (msec) is not provided directly, then these can be derived as : 
 If QTcB is machine read & RR is not provided, then :

ECG Parameters

$$RR = \left[\left(\frac{QT}{QTcB} \right)^2 \right] * 1000$$

[2] If QTcF is machine read and RR is not provided, then:

$$RR = \left[\left(\frac{QT}{QTcF} \right)^3 \right] * 1000$$

- If ECGs are manually read, the RR value preceding the measurement QT interval should be a collected value THEN do not derive.
- Important Note: Machine read values of RR should not be replaced with derived values.

Corrected QT Intervals

- When not entered directly in the eCRF, corrected QT intervals using Bazett's (QTcB) and Fredericia's (QTcF) formulas will be calculated, in msec, depending on the availability of other measurements.
- IF RR interval (msec) is provided then missing QTcB and/or QTcF will be derived as :

$$QTcB = \frac{QT}{\sqrt{\frac{RR}{1000}}}$$

$$QTcF = \frac{QT}{\sqrt[3]{\frac{RR}{1000}}}$$

- Important Note: Machine read values of QTcB and QTcF should not be replaced with re-derived values. If neither machine read QTcB or QTcF are available but QT and RR are collected, then a QTcB and QTcF can be derived however this should be discussed and agreed with the study team and the TLFs must have an appropriate footnote denoting those parameters are derived.

Adverse Events

AE's of Special Interest

- Liver events
- Cardiovascular events
- Potential systemic allergic reactions
- GI events
- Acetylcholinesterase (AChE) Inhibition

10.5. Appendix 5: Premature Withdrawals & Handling of Missing Data

10.5.1. Premature Withdrawals

Element	Reporting Detail
General	
 Subject study completion (i.e. as specified in the protocol) was defined as one who has completed all phases of the study including the follow-up visit. Withdrawn subjects may be replaced in the study. All available data from subjects who were withdrawn from the study will be listed and all available planned data will be included in summary tables and figures, unless otherwise specified.

10.5.2. Handling of Missing Data

Element	Reporting Detail
General	
 Missing data occurs when any requested data is not provided, leading to blank fields on the collection instrument : 
 These data will be indicated by the use of a “blank” in subject listing displays. Unless all data for a specific visit are missing in which case the data is excluded from the table. Answers such as “Not applicable” and “Not evaluable” are not considered to be missing data and should be displayed as such.
Outliers	
 Any subjects excluded from the summaries and/or statistical analyses will be documented along with the reason for exclusion in the clinical study report.

10.5.2.1. Handling of Missing Dates

Element	Reporting Detail
General	Partial dates will be displayed as captured in subject listing displays.
Adverse Events	
 The eCRF allows for the possibility of partial dates (i.e., only month and year) to be recorded for AE start and end dates; that is, the day of the month may be missing. In such a case, the following conventions will be applied for calculating the time to onset and the duration of the event: 
 Missing Start Day: First of the month will be used unless this is before the start date of investigational product; in this case the study treatment start date will be used (and hence the event is considered On-treatment as per Appendix 2: Treatment States and Phases). Missing Stop Day: Last day of the month will be used, unless this is after the stop date of study treatment; in this case the study treatment stop date will be used. Completely missing start or end dates will remain missing, with no imputation

Element	Reporting Detail
	
applied. Consequently, time to onset and duration of such events will be missing.
 
 Start or end dates which are completely missing (i.e. no year specified) will remain missing, with no imputation applied.

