Design Features	
 Phase I, multi-centre, single-dose, 3-part study. Part 1a: Approximately 27 subjects in a 3-period, cross-over study that will assess the relative bioavailability of gepotidacin in 2 free base tablet formulations (2 x 750 mg related compound (RC) [Treatment B] and high shear wet granulation (HSWG) tablets [Treatment C]) compared with the reference capsule formulations of gepotidacin (3 x 500 mg capsules [Treatment A]) under fasted conditions. Each subject will receive all 3 treatments according to their assigned treatment sequence based on a Latin square design (ABC, CAB, or BCA). Each cohort will contain 9 subjects. Based upon safety and pharmacokinetic (PK) data obtained from Part 1a, a decision will be made whether to use the free base RC or HSWG tablet formulation for Parts 1b and 2 Part 1b: Approximately 16 subjects in a 2-period, cross-over study that will evaluate the bioavailability of the selected tablet formulation under fasted and fed conditions. Each cohort will contain 8 subjects. Part 2: Approximately 10 Japanese subjects in a 2-period, fixed-sequence study that will evaluate the pharmacokinetics of a single dose of 1500 mg (2 x 750 mg) followed by a single dose of 3000 mg (4 x 750 mg) gepotidacin tablet formulation (RC or HSWG tablet) under fasted conditions. Part 3: Approximately 12 Japanese subjects stratified by gender, randomized to
-----------------	--

Overview of Study Design and Key Features	
	active or placebo in a 5:1 ratio in a 3-period, double-blind, placebo-controlled, fixed-sequence study that will evaluate the pharmacokinetics of a single dose of 1500 mg (2 x 750 mg), a single dose of 2250 mg (3 x 750 mg), and a single dose of 3000 mg (4 x 750 mg) gepotidacin tablet formulation (RC or HSWG tablet) selected from Part 1a or placebo under fed conditions.

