10.2. Appendix 2: Treatment States and Phases

10.2.1. Treatment States

Assessments and events will be classified according to time of occurrence relative to the start and/or stop date of the study treatment for the respective treatment period.

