10.2.1.2. Treatment States for AE Data

Treatment State	Definition
Pre-Treatment	AE Start Date/Time < Study Treatment Start Date/Time
On-Treatment	If AE onset date/time is on or after treatment start date/time & on or before the treatment stop date/time with 2 days lag time Study Treatment Start Date/Time ≤ AE Start Date/Time ≤ Study Treatment Stop Date/Time + 2 Days
Post-Treatment	If AE onset date/time is after the treatment stop date/time with 2 days lag time AE Start Date/Time > Study Treatment Stop Date/Time + 2 days
Onset Time	If Treatment Start Date/Time > AE Onset Date/Time = AE Onset Date - Treatment Start Date
Since First Dose (Days)	If Treatment Start Date/Time ≤ AE Onset Date/Time = AE Onset Date - Treatment Start Date +1 Missing otherwise
Duration (Days)	AE Resolution Date – AE Onset Date + 1
Drug-related	If relationship is marked 'YES' on eCRF OR value is missing

NOTES:

- If the study treatment stop date is missing then the AE will be considered to be On-Treatment.

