10.5.2.2. Handling of Partial Dates

Element	Reporting Detail
Concomitant Medications	
 Partial dates for any concomitant medications recorded in the eCRF will be imputed using the following convention: 
 If the partial date is a start date, a '01' will be used for the day and 'Jan' will be used for the month If the partial date is a stop date, a '28/29/30/31' will be used for the day (dependent on the month and year) and 'Dec' will be used for the month. The recorded partial date will be displayed in listings.
Adverse Events	
 Any partial dates for adverse events will be raised to data management. If the full date cannot be ascertained, the following assumptions will be made: 
 If the partial date is a start date, a '01' will be used for the day and 'Jan' will be used for the month. However, if these results in a date prior to Week 1 Day 1 and the event could possibly have occurred during treatment from the partial information, then the Week 1 Day 1 date will be assumed to be the start date. The AE will then be considered to start on-treatment (worst case). If the partial date is a stop date, a '28/29/30/31' will be used for the day (dependent on the month and year) and 'Dec' will be used for the month. The recorded partial date will be displayed in listings.

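### Read per period, the SAP's treatment-stop cap on a missing AE stop day forces duration to 1 day or less, and a second SAP rule gives a different stop date

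*SAP*

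**What the plan says.** SAP 10.5.2.1 expects incomplete AE dates: "The eCRF allows for the possibility of partial dates (i.e., only month and year) to be recorded for AE start and end dates". Its "conventions will be applied for calculating the time to onset and the duration of the event". A missing stop day becomes month-end, "unless this is after the stop date of study treatment; in this case the study treatment stop date will be used".

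SAP 10.2.1.2 defines duration as "AE Resolution Date – AE Onset Date + 1", so an event that resolves on its day of onset lasts 1 day. The same table defines an on-treatment AE: "If AE onset date/time is on or after treatment start date/time & on or before the treatment stop date/time with 2 days lag time". The SAP therefore expects onsets after the stop date.

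SAP 2.3 describes a "Phase I, multi-centre, single-dose, 3-part study". SAP 10.2.1 classifies events "relative to the start and/or stop date of the study treatment for the respective treatment period". Section 10.5.2.1 does not repeat that qualifier.

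SAP 10.5.2.2 has its own AE row. Partial dates first go to data management. If they stay unresolved, a partial stop date takes the final day of the month, with December supplied as the month, and there is no treatment-stop cap. The start-date bullet adds a reset: "However, if these results in a date prior to Week 1 Day 1". This study is organised in periods and days and has no Week 1. Nothing says which section governs.

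**The concern.** A cap at treatment stop may be workable when dosing continues for weeks. Here each period has one dose, so within a period treatment starts and stops on the same date. The cap then stops being an upper limit on an uncertain date. It becomes a fixed value on the dosing day, and many AEs will not yet have begun.

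The derived duration is at stake. It can take impossible values, and two programmers who each follow one section of the SAP would derive different stop dates for the same event.

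**Working it through.** The plan gives no figure to reproduce, so this is date arithmetic on its own rules.

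**Inputs**
- Duration = resolution - onset + 1 (SAP 10.2.1.2).
- One dose per period (SAP 2.3), so the period's stop date is the dosing date D.
- Washout of at least 3 days and follow-up 5 to 7 days after the final dose (Protocol 4.2). Minimum spacing puts doses on Days 1, 4 and 7. As a check, 30 days of screening + 7 + 7 = 44 days, the stated length of the three-period parts; 30 + 4 + 7 = 41 matches the two-period parts.

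**1. Stop date read per period.** Onset is D + k with k ≥ 0. Resolution cannot precede onset, so the end of the recorded month is on or after D. If it is later, the cap applies; if it equals D, the result is the same. The imputed stop is therefore always D, and

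duration = D - (D + k) + 1 = 1 - k.

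| Onset after dosing (days) | 0 | 1 | 2 | 3 | 7 |
|---|---|---|---|---|---|
| Imputed duration (days) | 1 | 0 | -1 | -2 | -6 |

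True length does not enter.

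**2. Stop date read as the last dose of the study.** With doses on Days 1, 4 and 7, and the recorded month ending after Day 7, onset on Day d gives 7 - d + 1 = 8 - d.

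| Onset day | 1 | 4 | 7 | 8 | 9 | 14 |
|---|---|---|---|---|---|---|
| Imputed duration (days) | 7 | 4 | 1 | 0 | -1 | -6 |

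Earlier-period AEs get a positive number set by the dosing calendar. Onsets after the last dosing day still get 0 or less.

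**3. The two sections on one record.** Assume a dose on 10 October 2017, onset on 11 October and resolution recorded as October 2017.
- 10.5.2.1, per period: 31 October is after 10 October, so stop = 10 October; 10 - 11 + 1 = 0 days.
- 10.5.2.2, recorded month kept: stop = 31 October; 31 - 11 + 1 = 21 days.

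**4. How often they agree.** Take every 2017 dose date, onset 0 to 7 days after dosing and resolution 0 to 7 days after onset: 365 × 8 × 8 = 23,360 combinations (the ranges are assumptions). Under the per-period reading, duration was 1 - k in all of them. The two sections agreed in 12 (12/23,360 = 0.05%), only when dosing fell on the last day of a month and the AE resolved that day. In 23% the 10.5.2.1 stop date fell outside the recorded month. These shares describe the grid and do not forecast the data.

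**5. After correction.** Same dose, taken as the final one, with last contact assumed on 17 October (7 days later). The stop is the earlier of 31 and 17 October, so 17 October. Onsets at +0, +1, +2 and +7 days give 8, 7, 6 and 1 days. Month-end alone would give 22, 21, 20 and 15. Both sets are upper bounds and neither is impossible.

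**The case against.** The strongest reply is that almost nothing depends on this. On-treatment status uses AE onset only. Tables 2.1 to 2.4, by their titles, report events, subjects and occurrences, not duration. Listings show the partial date as recorded. Subjects stay in the unit from Day -1 to Day 3 of the last period, and partial dates are queried, so few should remain. All of this stands. A derived duration might appear in the AE listing, but its shell is not among the documents.

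The reply also rules out several stronger readings that a reader might infer:

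- **Every affected record is wrong.** Not so. An AE that starts and resolves on the dosing day gets 1 day, which is correct. Such events are plausible: Protocol Tables 5 to 7 give median Tmax values of 1.25 to 3.0 hours, and Protocol 4.6.1 links cholinergic effects to Cmax.
- **The error always shortens events.** This holds only for the per-period reading. Under the last-dose reading, an AE that begins and ends on Day 1 could be given 7 days.
- **10.5.2.2 sends an October event to 31 December.** Taken literally it would (82 days in the example). But that section makes the day depend on month and year, which is needless if the month is always December. The natural reading is that December fills a missing month.
- **The conflict moves AEs between treatment columns.** This needs the parallel literal reading of January for start dates. For a start recorded in the month of first dosing or later, with that month kept and both anchors read as the first dose, the sections give the same start date.

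**Conclusion.** The point holds as a minor defect in wording. With the stop date read per period, which SAP 10.2.1 supports but 10.5.2.1 does not state, the rule gives 1 day for dosing-day onsets and 1 - k days, so 0 or less, for onset k ≥ 1 days after dosing. Under the last-dose reading the impossible values are limited to onsets after the final dosing day, and earlier-period durations are arbitrary. Neither reading gives a usable rule.

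The conflict with 10.5.2.2 is also real: month-end against the treatment stop date, with no precedence. It does not depend on the December wording.

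The damage is confined to derived durations in the few records whose stop day stays missing after query. No endpoint, estimate or planned AE summary table is shown to change.

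**What to change.** - In SAP 10.5.2.1, remove the treatment-stop cap. Use one rule for AE stop dates: keep the recorded month, impute the earlier of its last day and the follow-up or last-contact date, and never impute a date before onset. Let last contact include any extended follow-up of the event under Protocol 7.3.1.3, so that the date stays in the recorded month.
- In the AE row of 10.5.2.2, keep the instruction to raise partial dates to data management and the display of the recorded date in listings. Remove the start- and stop-date imputation bullets.
- Put the start-date rule in 10.5.2.1 only, anchored to the dose date of the study treatment in place of Week 1 Day 1. Say which period's dose is meant, and keep the existing condition that an on-treatment onset must be possible.

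The cost is SAP wording and the matching line of derivation code. No data collection, sample size or planned display changes.
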